Using a large sample, we will determine the psychometric properties of health questionnaires across levels of health literacy. Testing will be conducted in English and Spanish, across two modes of administration (paper-and-pencil vs. talking touchscreen). Each participant will have three visits (baseline, 3-month, and 6-month follow-up), described below, in order to determine changes in psychometric properties over time. We will use *differential item functioning* (DIF) and other psychometric analyses to identify questionnaire items with varying characteristics across levels of health literacy. Before the COVID-19 pandemic, our original plan was to recruit $N = 1216$ participants for in-person assessments. At the time of this plan our final N is 728 participants who have completed a health literacy assessment; some of these participants are missing data on subsequent questionnaires. In-person recruitment was put on hold during the COVID-19 pandemic; in order to adapt the the pandemic, a subset of participants ($N = 304$) was invited to a phone-based protocol that included data collection about the impact of COVID-19, vaccine confidence, and health-related quality-of-life (PROMIS-29 profile).

- **Develop alternative modes of test administration that can better accommodate people with low health literacy.** National statistics indicate that 14% of adults in the United States have below basic reading skills, and over 75 million Americans have below basic or basic health literacy skills.¹⁴ These data strongly indicate that many individuals seeking health care will have difficulties with written questionnaires, even those that have been carefully developed such as those in the NIH PROMIS. We will test an alternative mode of administration that has been specifically designed to aid people of low health literacy – a computer-assisted “talking” version that uses speech technology that participants can privately access as needed to have items and response options

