Data will be summarized by group and in total. In summary tables of continuous variables, the minimum, maximum, mean, and standard deviation will be presented with one decimal place. We will use counts and percentages in table for categorical variables. The denominator for each percentage will be the number of participants within the group unless otherwise specified. All hypothesis testing will be carried out at a two-tailed Type I error rate of $\alpha = .05$ unless otherwise specified. P-values will be rounded to three decimal places with a minimum of < 0.001 in tables. If statistical methods change during analysis, this will be documented in all reports with justification. Additional analyses of these data will be inevitable, but any exploratory analyses will be clearly marked as such.

Statistical power analysis and sample size selection

IRT and DIF analyses require large samples due to the large number of free parameters to be estimated. The proposed sample size herein is larger than other successful implementations of these same analyses carried out in other IRT studies.¹⁶⁻¹⁹ Moreover, we have carried out computer simulations to determine if our proposed sample sizes will be sufficient to create IRT models. We assumed a one-factor model across two groups at $n = 100$ each with standardized factor loadings set to .7 for eight questionnaire items. We used two groups for this simulation to ensure that any pairwise model comparisons would have adequate power. For this simulation, we specified that a non-significant model χ^2 was a good fit, which is a conservative decision because this particular test is highly sensitive relative to other measures of model fit, especially with large samples. Across 500 iterations, a good-fitting model was identified across groups 90% of the time. Even dropping the sample size to as low as $n = 50$ would identify a good-fitting model 84% of the time.

Missing data

We will describe the rate of missing data on an item-by-item basis using frequency tables in R. We do not anticipate high rates of missing data, but we will conduct subgroup analyses by health literacy, site, and administration mode as need to help diagnose any problems with missing data. For DIF analyses, IRT models

Table 1	
Visit 1 (Baseline)	Description of instrument
Language Assessment	To determine testing in English or Spanish
Single Item Health Literacy Screener	To screen for possible literacy status

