PROMIS Profile	To assess health-related quality of life.
PHQ-9	Self-report measure of depression.
Berlin Questionnaire (for sleep)	Self-report measure of sleep quality.
Purpose and Meaning (NIH Toolbox)	Self-report measure of the degree of meaning and purpose a person feels in their life.
RRS	Self-report measure of negative, repetitive thoughts.
PTSD Checklist	Self-report measure of posttraumatic stress disorder symptoms.
*C-SSRS Lifetime	Self-report measure of recent history of suicidal ideation and behavior. (This is not a variable of interest that will be used only to ensure patients' safety).
*C-SSRS Last Contact	Self-report measure of suicidal ideation and behavior since the individual's most recent assessment. (Used only as necessary to ensure patients' safety).
Exit Interview	

are estimated using full-information approaches that use all available data and can accommodate missing responses. We do not foresee a need for an imputation strategy, but if that were to become necessary, we will update this plan accordingly before running any analyses.

Study Design

This is a randomized experiment aimed at determining whether talking touchscreen technology can reduce DIF and provide a better testing experience, relative to paper-based testing. The original study design is shown below in Table 2, although as a result of the COVID-19 pandemic, we were unable to recruit all 1216 participants, but instead collected additional longitudinal data on a subset of participants ($n = 304$)

Table 2: Study Design			
Northwestern		BUMC	

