We hypothesize that DIF will be observed across adequate versus low levels of health literacy as measured by HealthLiTT.¹⁵ This hypothesis was formulated before any data were examined. In terms of direction, we predict that low-health-literacy groups will show lower item slopes. All questionnaires and subscales mentioned in the “Core battery for DIF Testing” section of protocol will undergo DIF testing. To examine DIF across health literacy status, we will conduct separate analyses within language and within testing format (paper-based vs. talking touchscreen). The overall N for these analyses, within strata, will be 304. We will use the *lordif* package in R for these analyses. This involves several steps. Four models are fit to the data (see Box 1). The models are regressions that link the probability of response type (e.g., “never”, “rarely”, “sometimes”, “often”, “always”) to a latent trait. If an item is free of DIF, then group (e.g., adequate vs. low health literacy) should have no effect. Thus, Model 2 and Model 3 should not fit significantly better than Model 1. It is well known that statistical significance is influenced, in part, by sample size. Thus, *lordif* uses effect-size measures to detect DIF, and to flag individual items where the effect of group exceeds a particular threshold. Effect sizes indicative of DIF will be chosen for each scale based on a Monte Carlo simulation carried out in *lordif*, which returns an effect size that would be unlikely given the null hypothesis of no DIF.

The following *a priori* decisions are important. We will use a Type I error rate of $\alpha = .01$ to generate the McFadden ΔR^2 effect size for each item that would be considered unusual if the null hypothesis of no DIF were true. Within each scale, we will select the smallest McFadden R^2 across all of the items. The minimum effect size we will consider

Box 1: Models fit by lordif

Model 0: $\text{logit}[P(Y \geq k)] = \alpha_k$
Model 1: $\text{logit}[P(Y \geq k)] = \alpha_k + \beta_1 (\text{ability})$
Model 2: $\text{logit}[P(Y \geq k)] = \alpha_k + \beta_1 (\text{ability}) + \beta_2 (\text{group})$
Model 3: $\text{logit}[P(Y \geq k)] = \alpha_k + \beta_1 (\text{ability}) + \beta_2 (\text{group}) + \beta_3 (\text{ability} \times \text{group})$

Note: α and β are logistic regression parameters. k refers to the number of thresholds needed for each item.

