$$\text{item slope}_j = a_j + b1_j * \text{Health LiTT} + b2_j * \text{Administration Type} + b3_j * \text{Interaction}$$

where j is an index for the k items (8 items in this case).

We will use Mplus in conjunction with the aMNLFA²⁴ package of R. Following the MNLFA procedure outlined by Curran et al.,²⁵ we will test models allowing item parameters (intercept and slope) to vary as a function of hypothesized DIF variable, one item at a time, in order to arrive at a final model. We will use the final model to generate item characteristics curves (ICCs, which will show the estimated probabilities of endorsement for each item across different levels of meaning and purpose. Among non-invariant items, we will consider differences (due to DIF variables) in probability endorsement of 10% to be potentially meaningful scientifically. Using the final model, we will also plot meaning and purpose factor scores by healthy literacy and administration type to understand the relationship among these variables. For these analyses, we will use all available baseline data collected through March of 2020 ($N = 566$ English speakers).

Longitudinal analyses of Meaning and Purpose Predicting Quality of Life. In addition to examining DIF by health literacy in the NIH Toolbox Meaning and Purpose measure (as described above), cross-lagged panel analyses will be used to examine whether meaning and purpose predicts health-related quality of life (i.e., anxiety, depression, fatigue, pain intensity and interference, physical function, sleep disturbance, and disruption of social roles and activities) over time across the three study assessments. We will also identify covariates including sociodemographics associated with meaning and purpose (i.e., age, gender, financial strain, education, race/ethnicity, language). We hypothesize that greater meaning and purpose will prospectively predict greater quality of life at subsequent study assessments. We will only include participants who could have provided complete data before we ceased recruitment due to COVID-19. Thus, we will exclude participants who are 1) were enrolled on or after 16 September 2020, and 3) missing their 6-month assessment. In this way, data will not be systemically missing due to censoring from the COVID-19 pandemic (i.e., to be eligible, the person would have had sufficient time to complete all three assessments before the COVID-19 pandemic).

Exit Interview

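### The SAP still gives 304 per primary DIF stratum, a figure from the abandoned target of 1216. With 728 participants at most two of the four strata can reach it, and the sample-size simulation does not address DIF detection.

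*SAP*

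**What the plan says.** Under Primary analyses, DIF by health literacy, the SAP compares low with adequate health literacy separately within each language and each testing format, which makes four strata. It states: "The overall N for these analyses, within strata, will be 304". Items are flagged by a McFadden R-squared change whose cut-off comes from a Monte Carlo null simulation at alpha .01: "Within each scale, we will select the smallest McFadden R^2 across all of the items", with a floor of .001. The hypotheses concern which items are flagged, how many, and whether fewer are flagged with the touchscreen than on paper.

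Other sections describe the sample differently. Study Design says of the pandemic period that "we were unable to recruit all 1216 participants". Study Objectives says: "At the time of this plan our final N is 728 participants who have completed a health literacy assessment", and adds that "some of these participants are missing data on subsequent questionnaires". Meaning and Purpose Analyses says: "For these analyses, we will use all available baseline data collected through March of 2020 ($N = 566$ English speakers".

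The sample-size section reports a simulation of a one-factor, eight-item model with all loadings at .7 in two groups of 100, where success is a non-significant model chi-square. It says: "We used two groups for this simulation to ensure that any pairwise model comparisons would have adequate power". The result is: "Across 500 iterations, a good-fitting model was identified across groups 90% of the time", falling to 84% at n = 50.

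**The concern.** The stratum size stated for the primary analysis cannot coexist with the final sample size given in the same current document. The shortfall is also unlikely to be even: the one language count available suggests that it falls mostly on the Spanish strata.

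This matters because the outcome is a list and count of flagged items. The flagging cut-off is simulated, so it rises as the sample shrinks. In a small stratum few items may be flagged simply because few can be. A reader who relies on 304 per stratum and on the power statement could take a short Spanish list as evidence of little literacy-related bias, when the data could not have shown otherwise. The power statement offers no protection, because the simulation behind it contains no group difference to detect.

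**Working it through.** **Inputs.** 304 per stratum and four strata (SAP, DIF by health literacy). Original target 1216, made up of 16 groups each split 38 paper and 38 touchscreen (Table 2). Final N 728, all with a health literacy assessment (Study Objectives). 566 English speakers (Meaning and Purpose Analyses). Simulation settings and results (sample-size section).

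**1. Reproducing 304.** One language and format stratum holds 8 groups x 38 = 304, and 4 x 304 = 1216. The figure is exactly 1216/4.

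**2. Against the final N.** No assumption is needed here, because literacy grouping requires the assessment that defines the 728.
- Shortfall: 1216 - 728 = 488, and 488/1216 = 40%.
- Mean per stratum: 728/4 = 182.
- 2 x 304 = 608, which is below 728, but 3 x 304 = 912, which is above it. At most two strata can reach 304, before any loss for missing questionnaires.

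**3. Split by language.** Assume that the 566 are among the 728 (their model uses Health LiTT as a predictor) and that formats are allocated 1:1, as in Table 2.
- English: 566/2 = 283 per format, 1 - 283/304 = 7% short.
- Spanish: at most 728 - 566 = 162, so at most 162/2 = 81 per format, 1 - 81/304 = 73% short.
- With an even literacy split (also assumed): 162/4, or about 40 per literacy group.
- Without 1:1 allocation, the smaller Spanish stratum still has 81 or fewer.
- Later English recruitment lowers the Spanish count. At 608 English speakers, Spanish falls to 120, or 60 per format.

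The phone subset also numbers 304, but the vaccine-confidence addendum says a coordinator read those questions aloud, so it is neither a paper nor a touchscreen stratum.

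**4. What the sample-size simulation measures.** I re-created it as a two-group, one-factor maximum-likelihood model with continuous indicators (an assumption; the SAP gives neither estimator nor indicator type).
- No DIF: the model was accepted 92% of the time at n = 100 per group and 87-88% at n = 50. The SAP reports 90% and 84%, so agreement is approximate.
- One loading lowered from .7 to .5 in one group: the model was still accepted 91% and 87% of the time. A test of equal loadings at alpha .05 found the difference only 19% and 13% of the time.

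The criterion rewards acceptance of a correct model and is blind to DIF.

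**5. What the SAP's own rule can detect.** This is illustrative, because the SAP states no target DIF size. Assumptions: 8 five-category graded-response items, loading .7 (slope 1.67), DIF in one item, equal trait means, known item parameters, no purification step, even literacy split, sparse categories collapsed. There were 3,000 null and 2,000 DIF replicates per setting.

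| | N=304 | N=283 | N=81 |
|---|---|---|---|
| Total-DIF cut-off | .0091 | .0096 | .0344 |
| Uniform test, shift 0.5 SD | 85% | 80% | 30% |
| Uniform test, shifts 0.3 to 0.7 SD | 37-99% | 34-99% | 8-55% |
| Non-uniform test, halved slope | 75% | 70% | 17% |

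The cut-off ratio .0344/.0091 = 3.8 is close to 304/81 = 3.75, as expected when a rule holds its false-positive rate. An unequal split of 24 and 57 at N=81 (assumed) gives 19% for the 0.5 SD shift and 15% for the halved slope. Repeat runs, some with fewer replicates, gave 85-89% at 304 and 26-30% at 81 for the 0.5 SD shift. For the halved slope they gave 75-79% and 17-30%. The halved-slope row holds the Box 1 intercepts fixed; if item difficulties are held fixed instead, power is about 2% at both sizes. The uniform result is therefore the steadier guide.

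**The case against.** The strongest reply is that this is one stale sentence. The SAP openly reports 728 and labels Table 2 as the original design. Recruitment is over, and the correction alters no model, threshold rule or hypothesis. The Monte Carlo cut-off adapts to the data analysed, so the false-positive rate does not depend on 304, and the paper-versus-touchscreen contrast is not biased by sample size. The English strata lose little.

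All of that stands, and it limits the problem to precision and interpretation. It does not make the stated N right, and precision is what a stated N is meant to convey.

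It is also fair that the Spanish count is inferred. No section gives a Spanish total or the actual format and literacy splits. Only the bound of two strata is free of assumptions. The power figures approximate the *lordif* procedure, and the halved-slope figure is sensitive to parametrisation.

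The sample-size section can be read as asking only whether IRT models can be fitted, which its simulation does address. But it also says the two-group set-up secures power for pairwise comparisons, and no other power evidence is offered.

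Finally, no section says that few flags will be read as no DIF, and calling the Spanish results descriptive is a judgement. The need for a precision caveat does not depend on that label.

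**Conclusion.** The concern holds. The figure of 304 is wrong for at least two of the four primary strata by arithmetic alone. If the 566 English speakers are among the 728 and formats are balanced, it is wrong for all four: modestly for English (about 283) and severely for Spanish (81 or fewer, at least 73% below the stated figure). The 90% and 84% in the sample-size section are acceptance rates for a correct model and give no support for power to detect DIF. Under the illustrative assumptions, a uniform shift of 0.5 SD that would be flagged about 85% of the time at 304 would be flagged about 30% of the time at 81, in either format. A short list of flagged Spanish items therefore cannot be read as absence of DIF, and the Spanish paper-versus-touchscreen comparison is imprecise though not biased by sample size. Exact sizes depend on counts the documents do not give. This should be corrected before the primary DIF results are reported.

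**What to change.** 1. Replace 304 with the actual N in each language, format and literacy cell, after missing questionnaires.
2. Delete the sentence on power for pairwise comparisons, or replace it with simulated power of the SAP's own *lordif* rule, including the smallest-threshold step, for a stated DIF size at those Ns. That step should be simulated as written: in the illustration it made the per-item error rate about .014-.021 instead of .01.
3. If the counts confirm small Spanish strata, state that their by-format DIF results, including any low count of flagged items, are descriptive because of low precision. Pooling the two Spanish formats could be added as a supplementary analysis but is not required.

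The cost is one corrected number, one deleted or replaced sentence, one caveat and, if power is to be claimed, one short simulation. The planned models stay as they are. The stated precision for Spanish speakers becomes less favourable.

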read to them. We will analyze the talking touchscreen groups and paper-based groups separately. We hypothesize that the talking touchscreen will reduce health literacy-related test bias by level of health literacy, relative to traditional paper-based methods. This will be evidenced by fewer items being flagged for DIF in the group that receives the talking touchscreen. In terms of descriptive statistics to display the magnitude of effects, we will report effect sizes (McFadden's R^2) of DIF items, as well as test characteristic curves (TCCs) for DIF items. Among participants with low health literacy, we expect that the discrimination parameters of the touchscreen condition will be higher than the paper-based condition.

- **Determine the degree of differential item functioning (DIF) of tools relevant to clinical research across different levels of health literacy.** DIF analyses will be conducted to identify test bias by level of health literacy. This will ensure that individuals with low literacy are assessed fairly in clinical and research settings. We will assess a broadly applicable instrument to primary care – the PROMIS Profile, which measures anxiety, depression, fatigue, pain interference, pain intensity, physical function, sleep disturbance, and social roles and activities. Other questionnaires included in the study are shown in Table 1. We will stratify participants into low versus adequate literacy levels using Health LiTT (groups will be formed according to T scores of < 55 vs. 55+).¹⁵ A secondary analysis will use the NUMI, a measure of health numeracy, in three groups (low = 0-3, medium = 4-6, high = 7 or greater). Then, we will determine whether psychometric properties of each questionnaire scale are consistent for individuals with low health literacy versus adequate health literacy. We hypothesize that DIF will be observed for multiple scales using paper-and-pencil administration, suggesting a need to improve test items, and a need to examine alternative ways to administer these tools.

Statistical methodology

Overview

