is .001. This effect size will then be used in *lordif* to detect items that show DIF. It should be noted that the simulation results from *lordif* would be a minimum, in which case we would need to choose larger (i.e., more conservative) effect sizes if *lordif* identifies a large number of items. In the event that more than 50% of items are flagged for DIF, we will re-run *lordif* with successive increases in .005 increments in the DIF detection criterion. This will allow us to identify which items produce the highest R^2 values consistently, regardless of the *a priori* R^2 DIF detection criterion

We will compile a list of items flagged for uniform (Model 1 vs. 2 from Box 1), non-uniform (Model 2 vs. 3), and total DIF (Model 1 vs. 3). Our *a priori* hypothesis is that DIF will be observed across levels of health literacy for paper-based testing. We further hypothesize that DIF will also be found for the talking touchscreen, but for fewer items. In addition, we hypothesize that the magnitude of each DIF item’s ΔR^2 value will be larger in the paper-and-pencil group relative to the touch-screen group.

In addition to testing these specific hypotheses, we will create reports of descriptive statistics. For each item flagged for DIF, we will, 1) report the ΔR^2 values associated with uniform and non-uniform DIF, 2) summarize all IRT parameters across groups, 3) inspect the magnitude of θ versus a DIF-purified θ (see reference²³ for computational details) on a participant-by-participant basis to determine the practical effects of DIF, and 4) evaluate test characteristics curves (TCCs) to determine the effect of DIF on the overall test score.

In addition to scale-by-scale analyses, we will conduct exploratory analyses of questionnaires together (e.g., PROMIS depression together with PHQ-9, PROMIS sleep and Berlin), to explore the power of DIF analyses using multiple scales of the same construct.

Prediction of depression: Health literacy as a moderator of rumination, pain, fatigue, and sleep disturbance

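### The planned DIF analysis matches on each scale's own trait, so it cannot see literacy bias shared by most or all items, and no cross-mode test is specified for the core scales to fill that gap

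*SAP*

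**What the plan says.** SAP, Primary analyses, DIF by health literacy: items are analysed scale by scale in lordif, separately within language and within administration mode. "The models are regressions that link the probability of response type" to a latent trait. In Box 1, Model 1 contains the trait alone, Model 2 adds literacy group, and Model 3 adds the trait x group product. The reading given is: "If an item is free of DIF, then group (e.g., adequate vs. low health literacy) should have no effect".

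The flagging threshold comes from a Monte Carlo null at a .01 error rate: "Within each scale, we will select the smallest McFadden R^2 across all of the items", with a floor of .001. "In the event that more than 50% of items are flagged for DIF", the threshold is raised in steps of .005. The practical check compares each participant's trait score with its DIF-purified version. No external criterion and no pre-named anchor items are given.

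SAP, Study Objectives: the benefit of the talking touchscreen is to be judged by a count. "This will be evidenced by fewer items being flagged for DIF in the group that receives the talking touchscreen". Of the DIF work in general the SAP says: "This will ensure that individuals with low literacy are assessed fairly in clinical and research settings".

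Three parts of the SAP touch on the comparison of modes:
- Study Objectives expects higher discrimination on touchscreen than on paper among low-literacy participants. No model or test is given.
- Meaning and Purpose Analyses plans a moderated nonlinear factor analysis (MNLFA) with literacy, mode and their interaction, and a plot of factor scores by literacy and mode. It covers one 8-item scale in English speakers.
- Study Timepoints expects acceptable factor-model fit on touchscreen and unacceptable fit on paper, with each mode fitted separately.

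**The concern.** The matching variable is built from the items under test. If poor reading moves most items of a scale the same way, the movement enters the trait estimate and looks like a true difference between literacy groups. The few unaffected items then look biased. Purification anchors on the unflagged items, so it has the same limitation.

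At stake is the trial's own question. A paper scale distorted throughout for low-literacy readers could be reported as almost free of DIF. A touchscreen that removed the distortion, or left it in only one or two items, could then appear to give no benefit or to do worse. The SAP's predicted direction, lower item slopes in low-literacy groups, is not limited to a few items, so the scale-wide case cannot be set aside.

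**Working it through.** **1. The plan's own figures.** The SAP power section reports a good-fitting two-group one-factor model in 90% of runs at n = 100 per group and 84% at n = 50 (8 items, loadings .7). A re-run with 2,000 replicates gave 90.6% and 86.9% (configural model), and 91.4% and 86.4% (metric model). The 90% reproduces. The 84% is 2.4 to 2.9 points off, about 1.5 to 1.8 Monte Carlo standard errors of a 500-run simulation. The simulation contains no DIF, so it does not bear on this point.

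Stratum size: 2 sites x 2 literacy x 2 sex x 38 = 304, or 152 per literacy group, as the SAP states. At the final N of 728 the average stratum is 728/4 = 182, or 91 per literacy group.

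**2. Why common bias is absorbed.** Write the graded model as logit P(Y ≥ k) = a_j(θ − b_jk).
- If every item shifts by c on the trait in the low-literacy group, it becomes a_j(θ + c − b_jk). This is the unbiased model with θ' = θ + c.
- If every slope is multiplied by r with intercepts unchanged, a_jθ becomes a_j(rθ). This is the unbiased model with θ' = rθ, a smaller trait variance.

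In both cases literacy group adds nothing once θ' is in the model.

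**3. Emulation of the planned procedure.** Steps: pooled graded response model, EAP trait score, Models 1 to 3, McFadden ΔR² of Model 1 versus 3, the smallest item 99th percentile from 500 null runs as threshold (0.0076 at 152 per group), iterative purification, then the more-than-50% rule; 150 replicates per scenario. Assumptions not in the documents: 8 items with 5 categories; slope 1.7 x .7/√(1 − .49) = 1.67; no true trait difference; equal, same-direction bias; flagging on total DIF. A shift of 0.8 logit is 0.8/1.67 = 0.48 trait SD.

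Shift of 0.8 logit, 152 per literacy group:

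| Biased items of 8 | Biased flagged | Clean flagged | Mean flags | False trait difference (SD) |
|---|---|---|---|---|
| 0 | – | 2% | 0.20 | – |
| 1 | 85% | 4% | 0.85 + 7 x 0.04 = 1.13 | – |
| 2 | 77% | 5% | 1.83 | 0.08 |
| 3 | 60% | 8% | 2.20 | 0.16 |
| 4 | 34% | 26% | 2.41 | 0.20 |
| 5 | 13% | 53% | 2.24 | 0.27 |
| 6 | 7% | 73% | 1.89 | 0.33 |
| 7 | 4% | 80% | 1.05 | 0.40 |
| 8 | 3% | – | 0.24 | 0.44 |

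From 4 biased items up, every flagged clean item was flagged in the reverse direction. The more-than-50% rule came into play in at most 3% of these runs.

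Other scenarios (biased / clean flagged):
- Slopes x 0.6, 152 per group: 34% / 3% (2 items), 21% / 12% (4), 9% / 36% (6), 3% (8, with a trait SD ratio of 0.70).
- Shift of 0.5 logit, 152 per group: 32% / 4% (2), 5% / 30% (6), 3% (8).
- Shift of 0.8 logit, 91 per group: 36% / 3% (2), 3% / 30% (6), 2% (8).

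**4. What the randomised modes could show.** Low-literacy participants, paper with all 8 items shifted versus unbiased touchscreen, two-sided .05. With n per arm, the simple contrast has noncentrality d√(n/2). The mode x literacy interaction has this divided by √2.

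| Shift | d | n per arm | Simple contrast | Interaction |
|---|---|---|---|---|
| 0.8 logit | 0.43 | 152 | 0.96 | 0.75 |
| 0.8 logit | 0.43 | 91 | 0.82 | 0.53 |
| 0.8 logit | 0.43 | about 40 | 0.48 | 0.27 |
| 0.5 logit | 0.29 | 152 | 0.70 | 0.42 |
| 0.5 logit | 0.29 | 91 | 0.49 | 0.28 |

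The row at about 40 is for Spanish speakers: with 566 English speakers among 728, at most 162 remain, and 162/4 ≈ 40 per literacy-by-mode cell if evenly split.

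With all slopes x 0.6, the mean contrast has d = 0.00 and power 0.03. The score SD ratio is 0.73, and a variance test at 152 per arm has power 0.97.

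**The case against.** The strongest reply is that this is a general property of internally anchored DIF methods and that the SAP is not inconsistent on it. That is right. A reader might take the sentence on group having no effect as an unconditional null. The text around it refers to a latent trait, and every group term in Box 1 sits beside ability, so the stated null is conditional on trait.

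The SAP also expects faults in individual items: it speaks of a need to improve test items. With up to 3 of 8 items biased, the method mainly flags the right ones. No passage establishes that poor reading affects all items alike. This limits how often the problem would arise, but it does not make flag counts informative when it does.

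Nor is the comparison of modes absent. The discrimination expectation, the MNLFA and the contrast in factor-model fit are all in the plan. They do not close the gap. The first has no test. The second covers one scale in one language and frees items one at a time. The third is fitted within mode and would also absorb a fully common shift.

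Finally, a randomised contrast shows only the difference in bias between modes. Bias common to both stays unseen. A simple difference cannot say which mode is biased, or separate a general mode effect from literacy bias. These limits stand and must be stated with any added test.

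**Conclusion.** The point holds in a limited form. lordif as planned detects bias relative to the rest of the scale. Once more than half the items share similar, same-direction bias, biased items go largely unflagged and clean ones are flagged in reverse. When all items are biased, or all slopes fall in proportion, almost nothing is flagged (3%). A fully biased paper arm averages 0.24 flags against 1.83 for a touchscreen arm with two biased items, so the planned criterion can reverse the conclusion. Flag counts therefore cannot support the claim that fair assessment is ensured.

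Absorption of scale-wide bias follows from the model and does not depend on the simulation. The percentages do rest on the assumed item number, slope, shift size and uniform bias.

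Two stronger readings are not supported. One is that clean items are generally flagged in place of biased ones: this needs most but not all items to be biased. The other is that the SAP ignores the comparison of modes: what is missing is a specified cross-mode test for the core scales.

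**What to change.** For each scale, within language and among low-literacy participants, pre-specify a two-group graded response model for paper versus touchscreen. Hold the latent mean and variance equal across modes, which randomisation justifies as long as literacy group and completion do not depend on assigned mode. Test equality of all thresholds and equality of all slopes. Support this with a mode x literacy test of the scale score. The score test must not stand alone, because it has no power against pure slope loss.

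Label these analyses supportive and state a multiplicity rule. Add that the contrast identifies only bias that differs between modes, that bias common to both stays unseen, and that lordif alone cannot show a scale is fair. Soften the sentence in Study Objectives on ensuring fair assessment to match.

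Cost: no new data. SAP, Health questionnaires lists 7 PROMIS domains, Berlin, Meaning and Purpose, the PTSD checklist, 3 RRS scores and PHQ-9, which makes 14 scales or subscales. At 3 tests each in 2 languages this is up to 14 x 2 x 3 = 84 extra tests. Power is limited in Spanish speakers, where a null result should not be read as absence of bias. The power figures above are for score contrasts; power of the two-group model was not simulated.
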